### **8.1.2.5 PGIC**

The PGIC is a 2-state, self-report measure that reflects a participant's assessment of overall change in their PD symptoms and overall fatigue since they started taking the study medication. The PGIC is a 7-point scale (“much improved,” “moderately improved,” “a little bit improved,” “no change,” “a little bit worse,” “moderately worse,” “much worse”).

### **8.1.2.6 HADS**

The Hospital Anxiety and Depression Scale (Zigmond and Snaith, 1983) is a patient-administered questionnaire that consists of 2 subscales for anxiety and depression. Each subscale consists of 7 items which are scored separately on a 4-point (0–3) scale, leading to a total score range from 0 to 21 for each of the 2 subscales.

### **8.1.2.7 EQ-5D-5L**

The EQ-5D-5L consists of 2 pages: the EQ-5D descriptive system and the EQ visual analogue scale (EQ-VAS).

The descriptive system comprises 5 dimensions: mobility, self-care, usual activities, pain/discomfort, and anxiety/depression. Each dimension has 5 levels: “no problems,” “slight problems,” “moderate problems,” “severe problems,” and “extreme problems”. The study participant is asked to indicate his/her health state by ticking the box next to the most appropriate statement in each of the 5 dimensions. This decision results in a 1-digit number that expresses the level selected for that dimension. The digits for the 5 dimensions can be combined into a 5-digit number that describes the study participant's health state.

The EQ-VAS records the study participant's self-rated health on a vertical visual analogue scale, where the endpoints are labeled ‘The best health you can imagine’ and ‘The worst health you can imagine.’ The VAS can be used as a quantitative measure of health outcome that reflects the study participant's own judgement.

### **8.1.3 Wearable sensor**

Data generated from the wearable sensor will be included within the panel of exploratory assessments and comprise changes in objective measures of motor function, sleep, and selected neurovegetative parameters assessed with a customized, wrist-worn digital sensor (hereinafter referred to as “wearable sensor,” which will be worn on the usual wristwatch side for comfort,

even if it is not the most affected side). The multisensor unit will continuously collect physiological and environmental data, including acceleration/orientation, pulse rate, skin impedance, ambient pressure, ambient temperature (in device chamber), and ambient light level.

Digital data collection is initiated during an approximately 2-week adaptation period (Section 1.3) to address technical issues and handling errors and to ensure robust Baseline data before initiation of dosing. Where it is not possible to access the sensor during the Baseline period, participants may start wearing it until Visit 8 (M4). To yield a solid Baseline for the VMEs, these home-based structured activities will be conducted every day throughout the familiarization period. If necessary, the frequency will be adjusted on an individual basis. Study participants will be encouraged to identify a most appropriate time-window in their daily schedule, where the home-based structural activities should be placed. This routine should be maintained until the end of the study. In case of initiation of symptomatic treatment, the home-based VME should be conducted in the practically defined off-state (typically before the intake of the morning medication). Throughout the first 12 months of the study, spontaneous activity data coming from the various sensors included in the wearable sensor will be continuously (up to 23 hours/day) collected in a usual home-setting (or work setting, if applicable) and throughout all non-home-based activities. Even though the laterality of the most pronounced motor symptoms should shift to the contralateral side over time, the wearable sensor will continue to be worn on the initially selected side. In addition to the continuous data collection, a series of 8 simple structured motor tasks will be performed on a weekly basis in the study participant's home environment.

### **Screening Period (Visit 2 to Visit 3):**

During the Screening Period between Visit 2 and Visit 3 (or any 2-week period before Visit 9 [M6] for participants consenting to using the wearable sensor after having completed the Screening Period), one VME per day will be performed by the participants at home to familiarize themselves with the wearable sensor. Participants will rate their individual performance of each VME Skill Check directly on the wearable sensor after each task (5-option smiley face scale, with description provided in the VME training guide).

### **Baseline (Visit 3):**

During the Baseline Visit (Visit 3), participants will perform the VME in the clinic before the first dose of the study treatment, following the MDS-UPDRS Part III assessments. Investigators will rate participant performance of each VME Skill Check following the Investigator Rating Scale (refer to Section 10.12 [Appendix 12]).

The frequency of the VME will be changed after the familiarization period to weekly on the wearable sensor by the Investigator at the next clinical study visit. Participants will be requested to select the day of the week and the time to plan the VME Skill Check Schedule.

### **Treatment Period:**

At clinic visits and during telemedicine visits when MDS-UPDRS is assessed, the participants will perform 1 VME, back-to-back after their MDS-UPDRS Part III assessments. Each VME task will be scored by the Investigator.

The participant will also be asked to perform 1 VME per week at home, first thing in the morning before intake of any PD treatment.

The wearable sensors will be finally returned by the participant to the site on Visit 15 (M18) or Early Termination Visit in case of early study termination).

## 8.2 Safety assessments

Planned time points for all safety assessments are provided in the Schedule of Activities (Section 1.3).

### 8.2.1 Physical examination

Physical examinations will be performed at the scheduled time points presented in the Schedule of Activities (Section 1.3). A complete physical examination will include, at a minimum, general appearance; ear, nose, and throat; eyes, hair, and skin; and assessments of the cardiovascular, respiratory, gastrointestinal, musculoskeletal, hepatic, and neurological systems (including sensation, muscle strength, reflexes, balance, and mental state) (a brief neurological exam will only be performed as part of the physical assessment on days when the full neurological exam is not already scheduled).

A brief physical examination will include, at a minimum, assessments of the skin, lungs, cardiovascular system, and abdomen. A physical examination of the skin will include, at a minimum, a visual check of the skin (including an inspection of the oral cavity), and may be conducted by a nurse or physician. Investigators and site staff should pay special attention to clinical signs related to previous serious illnesses and hypersensitivity reaction (such as rash, angioedema, or anaphylaxis). For any emergent lesion or abnormality on the skin, a full examination of skin and close observation is required to exclude possibility of a hypersensitivity reaction as per Section 8.3.6.1.

During telemedicine video call visits, physical examinations will be limited to focused body examinations performed by research nurses. These will include, at a minimum, an assessment of the cardiovascular system (absence/presence of swelling of feet/ankles, absence/presence of pallor), respiratory system (absence/presence of cyanosis), gastrointestinal system (absence/presence of ulcers, rash, lumps, or exudate in the mouth, absence/presence of jaundice, absence/presence of abdominal pain on palpitation), and skin (absence/presence of rash, ulcers, lumps). The examination by the nurses will be guided and assessed by the Investigator via telemedicine video call.

Any abnormal finding from the focused body examinations by the research nurses will be highlighted to the Investigator. The research nurses should pay special attention to clinical signs related to previous serious illnesses and hypersensitivity reaction (such as rash, angioedema, or anaphylaxis). Any abnormal findings, specifically skin changes potentially related to hypersensitivity reaction (such as rash, angioedema, or anaphylaxis) (Section 8.3.6.1), should be highlighted to the Investigator and should be photographically documented, if the participant provides consent. The Investigator will provide instructions regarding further activities. Any abnormal finding from the focused body examinations by the research nurses will be highlighted to the Investigator.

Clinically relevant findings or worsening of previous findings will be recorded as AEs.

Height and weight will be measured and recorded at the Screening Visit, and the study participant's BMI will be calculated. Height will be measured with the study participant not wearing shoes and the outcome will be rounded to the nearest 1cm. Body weight will be

measured with the study participant wearing light clothing and without wearing shoes; the outcome will be rounded to the nearest 0.1kg. The BMI will be calculated (weight [kg]/[height (m^2)]) and will be reported to 1 decimal place.

### **8.2.2      Neurological examination**

The complete neurological examination will include selected assessment of general neurological status (level of consciousness, mental status, speech), cranial nerves, reflexes, motor system (general motor status, muscle strength, muscle tone), coordination/cerebellar function, and sensation. The day before or the day of the lumbar puncture, a complete neurological examination should be performed in accordance with local safety procedures and results should be available prior to performing the lumbar puncture. Clinically significant neurological examination findings are to be reported as AEs.

A brief neurological exam will include, at a minimum, assessment of the general neurological status (level of consciousness, mental status, speech), reflexes, and motor system (general motor status, muscle strength, muscle tone).

During telemedicine video call visits, neurological examinations will be limited to focused neurological examinations performed by the research nurses. These will include, at a minimum, determination of the level of consciousness, major psychopathological abnormalities, motor function, sensation, cerebellar function, muscle reflexes, and cranial nerve function. Study participants will be actively encouraged to verbally describe any neurological changes they have experienced since the last visit. This information will be captured by the nurse. Any significant new abnormal findings emerging on the brief neurological examination may entail a more formal investigation by a trained neurologist for accurate characterization and determination of the level of consciousness, major psychopathological abnormalities, motor function, sensation, cerebellar function, muscle reflexes, and cranial nerve function. The examination by the nurses will be guided and assessed by the Investigator via telemedicine video call.

### **8.2.3      Vital signs**

Vital signs, including pulse rate, systolic blood pressure (SBP), diastolic blood pressure (DBP), respiratory rate, and tympanic body temperature will be measured with a completely automated device after 5 minutes of rest in supine position (in a quiet setting without distractions such as a television or cell phones) and erect to assess autonomous dysregulation. Manual techniques will be used only if an automated device is not available. Any observation by the research nurse will be discussed with the investigator during the video communication part of the remote visit. Any clinically significant abnormality in the view of the Investigator will be recorded as an AE.

Vital signs (to be taken before blood collection for laboratory tests) will consist of 3 pulse and 3 blood pressure (BP) measurements (3 consecutive BP readings will be recorded at intervals of at least 1 minute). All pulse and BP readings will be recorded on the eCRF and the average will be derived for analyses.

### **8.2.4      Electrocardiograms**

Triplicate 12-lead ECGs will be obtained as outlined in the Schedule of Activities (see Section 1.3) using an ECG machine that automatically calculates the heart rate and measures PR,

QRS, QT, and QTcF intervals. Refer to Section 7.1.3 for QTcF withdrawal criteria and any additional QTc readings that may be necessary.

The study participant should be resting in the supine position for at least 10 minutes before the start of the recordings. At each time point at which triplicate ECG are required, 3 individual ECG tracings should be obtained as closely as possible in succession, but no more than 2 minutes apart. The full set of triplicates should be completed in less than 10 minutes. Electrocardiograms will be obtained by the research nurse during remote visits. Any observation by the research nurse will be discussed with the Investigator during the video communication part of the remote visit.

The Investigator should review all ECG recordings and, if there are abnormalities that are considered clinically significant for a particular study participant, then the Investigator should initiate a review by a specialist of all ECG data pertaining to that study participant. The following ECG parameters will be recorded in the eCRF: heart rate, PR interval, QRS duration, QT interval, QTcF, and Investigator's conclusion on ECG profile.

### **8.2.5 Clinical safety laboratory assessments**

See Appendix 2 (Section 10.2) for the list of clinical laboratory tests to be performed and the Schedule of Activities (Section 1.3) for the timing and frequency. Blood/urine sampling and urine pregnancy testing will be performed by the research nurses during remote visits.

The Investigator must review the laboratory report, document this review, and record any clinically relevant changes occurring during the study in the AE section of the eCRF. The laboratory reports must be filed with the source documents. Clinically significant abnormal laboratory findings are those which are not associated with the underlying disease, unless judged by the Investigator to be more severe than expected for the participant's condition.

All laboratory tests with values considered clinically significantly abnormal during participation in the study or within 30 days after the last dose of study medication should be repeated until the values return to normal or Baseline or are no longer considered clinically significant by the Investigator or Medical Monitor.

If such values do not return to normal/Baseline within a period of time judged reasonable by the Investigator, the etiology should be identified and the Sponsor notified.

All protocol-required laboratory assessments, as defined in Appendix 2 (Section 10.2), must be conducted in accordance with the laboratory manual and the Schedule of Activities (Section 1.3).

If laboratory values from non-protocol specified laboratory assessments performed at the institution's local laboratory require a change in participant management or are considered clinically significant by the Investigator (eg, SAE or AE), then the results must be recorded in the eCRF.

### **8.2.6 Suicidal risk monitoring**

UCB0599 is a CNS-active study medication. There has been concern that some CNS-active study medications may be associated with an increased risk of suicidal ideation or behavior when given to some participants with PD.

Suicidality will be assessed by trained site study personnel using the C-SSRS (Posner et al, 2011). During remote visits, the assessment will be performed remotely via telemedicine. This scale will be used for Screening as well as to assess suicidal ideation and behavior that may occur during the study. All study participants will complete the “Baseline/Screening” version of the C-SSRS at Visit 1 (assessing the past 6 months), followed by the “Since Last Visit” version at the visits indicated on the Schedule of Activities (Section 1.3).

Participants being treated with UCB0599 should be monitored appropriately and observed closely for suicidal ideation and behavior or any other unusual changes in behavior. Families and caregivers of participants being treated with UCB0599 should be instructed to monitor participants for the emergence of unusual changes in behavior, as well as the emergence of suicidal ideation and behavior, and to report such symptoms immediately to the study Investigator. Consideration should be given to discontinuing UCB0599 in participants who experience signs of suicidal ideation or behavior. Study stopping behavior for study participants with suicidal ideation or behavior is described in Section 7.2.

#### **8.2.7 MRI assessments**

Structural brain MRIs will be performed at the Screening Visit (Visit 2) for study participants without an acceptable historical scan within 6 months before this visit, on an MRI scanner of at least 1.5 Tesla, using a standardized acquisition protocol and without contrast. At a minimum, the following sequences will be performed per local standard practice: T1, T2, and T2 FLAIR.

#### **8.2.8 Wearable sensor data**

Physiological and environmental data obtained from the wearable sensor will not be used for safety monitoring and reporting of UCB0599 because the sensor is unvalidated for this purpose and will be only used for exploratory endpoints in this study.

The Investigator is expected to record any AEs in the eCRF and assess causality as it might relate to the wearable sensor. The eCRF page will allow the Investigator to assess causality in relation to the wearable sensor.

Serious adverse events should be reported in the eCRF and expedited to the Sponsor according to Appendix 3 (Section 10.3).

The Sponsor will send reports of SAEs relating to the wearable sensor to Verily so that the manufacturer can comply with its reporting obligations.

See Appendix 7 (Section 10.7) for more information about sensor deficiencies, accountability, handling, and discontinuation.

#### **8.3 Adverse events and serious adverse events**

The definitions of an AE or SAE can be found in Appendix 3 (Section 10.3).

Adverse events will be reported by the participant (or, when appropriate, by a caregiver or surrogate).

The Investigator and any designees are responsible for detecting, documenting, and recording events that meet the definition of an AE or SAE and remain responsible for following up AEs that are serious, considered related to the study medication or study procedures, or that caused the participant to discontinue UCB0599 or PD0053 (see Section 7).

On the AE eCRF page, there is the possibility to assess causality to the IMP and to any concomitant medication. If an AE is considered related to COVID-19 vaccine, a causality assessment should be entered in the AE eCRF.

Note that in this case the national recommendation for reporting AEs related to COVID-19 vaccines should be followed.

If an AE is the result of an interaction between a COVID-19 vaccine and IMP in the study, then the clinical study causal association should be for both IMP and COVID-19 vaccine.

For results disclosure on public registries (eg, ClinicalTrials.gov), TEAEs and treatment-emergent SAEs will be published.

### **8.3.1 Time period and frequency for collecting AE and SAE information**

All AEs and SAEs will be collected from the signing of the ICF until the SFU Visit at the time points specified in the Schedule of Activities (Section 1.3).

In order to ensure complete safety data collection, all AEs occurring during the study (ie, after the signing of the ICF), including any pretreatment and posttreatment periods required by the protocol, must be reported in the eCRF even if no study medication was taken but specific study procedures were conducted. This includes all AEs not present prior to the initial visit and all AEs that recurred or worsened after the initial visit.

All SAEs will be recorded and reported to the Sponsor or designee within 24 hours, as indicated in Appendix 3 (Section 10.3). The Investigator will submit any updated SAE data to the Sponsor within 24 hours of it being available.

The Investigator is specifically requested to collect and report to UCB (or its representative) any SAEs (even if the Investigator is certain that they are in no way associated with the study medication), up to 30 days from the end of the study for each participant, and to also inform participants of the need to inform the Investigator of any SAE within this period. Serious AEs that the Investigator thinks may be associated with the study medication must be reported to UCB regardless of the time between the event and the end of the study.

The method of recording, evaluating, and assessing causality of AEs and SAEs and the procedures for completing and transmitting SAE reports are provided in Appendix 3 (Section 10.3).

### **8.3.2 Method of detecting AEs and SAEs**

Care will be taken not to introduce bias when detecting AEs and/or SAEs. Open-ended and non-leading verbal questioning of the participant is the preferred method to inquire about AE occurrences.

### **8.3.3 Follow-up of AEs and SAEs**

After the initial AE/SAE report, the Investigator is required to proactively follow each participant at subsequent visits/contacts. All SAEs, and nonserious AESIs (as defined in Section 8.3.6) will be followed until resolution, stabilization, the Investigator determines that it is no longer clinically significant, the event is otherwise explained, or the participant is lost to follow up (as defined in Section 7.3). Further information on follow up procedures is given in Appendix 3 (Section 10.3).

### **8.3.4 Regulatory reporting requirements for SAEs**

Prompt notification by the Investigator to the Sponsor of an SAE is essential so that legal obligations and ethical responsibilities towards the safety of participants and the safety of a study medication under clinical investigation are met.

The Sponsor has a legal responsibility to notify both the local regulatory authority and other regulatory agencies about the safety of a study medication under clinical investigation. The Sponsor will comply with country-specific regulatory requirements relating to safety reporting to the regulatory authority, Institutional Review Boards (IRB)/Independent Ethics Committees (IEC), and Investigators.

Investigator safety reports must be prepared for suspected unexpected serious adverse reactions according to local regulatory requirements and Sponsor policy and forwarded to Investigators as necessary.

An Investigator who receives an Investigator safety report describing a SAE or other specific safety information (eg, summary or listing of SAEs) from the Sponsor will review and then file it along with the IB and will notify the IRB/IEC, if appropriate according to local requirements.

### **8.3.5 Pregnancy**

Details of all pregnancies in female participants and, if indicated, female partners of male participants will be collected after the start of study medication and until at least 12 months after the delivery date.

If a pregnancy is reported, the Investigator must immediately inform the Sponsor within 24 hours of learning of the pregnancy and should follow the procedures outlined in Appendix 4 (Section 10.4).

The participant should be withdrawn from the study as soon as pregnancy is known (by positive pregnancy test), and the following should be completed:

- The participant should return for an early discontinuation visit.
- The participant should immediately stop the intake of the study medication as instructed at the early discontinuation visit.
- An SFU Visit should be scheduled 14 days after the participant has discontinued her study medication.

Abnormal pregnancy outcomes (eg, spontaneous abortion, fetal death, stillbirth, congenital anomalies, ectopic pregnancy) are considered SAEs.

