BL=Baseline; BP=blood pressure; C-SSRS=Columbia Suicide Severity Rating Scale; CGI=Clinical Global Impression of Improvement; CGIS=Clinical Global Impression of Severity; COVID-19=coronavirus disease-2019; CSF=cerebrospinal fluid; D=Day; DaT-SPECT=Dopamine Transporter Imaging With Single Photon Emission Computed Tomography; DNA=deoxyribonucleic acid; ECG=electrocardiogram; EDC=electronic data capture; EQ-5D-5L=Euro Quality of life 5-Dimensions 5-Level; EOT=End of Treatment; FSH=follicle stimulating hormone; H&Y=Hoehn and Yahr; HADS=Hospital Anxiety and Depression Scale; HbA1c=hemoglobin A1c; HIV=human immunodeficiency virus; ICF=Informed Consent form; IgE=Immunoglobulin E; IRT=interactive response technology; M=Month; MDS-NMS=Movement Disorder Society Non-motor Scale; MDS-UPDRS=Movement Disorder Society-Unified Parkinson's Disease Rating Scale; MoCA=Montreal Cognitive Assessment; MRI=magnetic resonance imaging; PD=Parkinson's Disease; PGIC=Patient Global Impression of Change; PGIS=Patient Global Impression of Severity; PK=pharmacokinetic(s); PRO=patient-reported outcomes; RNA=ribonucleic acid; SE-ADL=Schwab and England Activities of Daily Living; SFU=Safety Follow-up; ST=symptomatic treatment; V=Visit; VME=Virtual Motor Exam

  Telemedicine video call with attending research nurse at the participant's home

 Clinic visit

a Visit 2 should be conducted only when Visit 1 assessment results are available. Visit 2 assessments can be conducted on 2 consecutive or nonconsecutive days.

b Visits are in-clinic only in France. Therefore, details on telemedicine visits are not implemented (for France-specific requirements, please refer to Section 10.9, Appendix 9).

c All study participants prematurely terminating from the study should be encouraged to undergo final evaluation procedures in accordance with the EOT and SFU Visit schedule (30 days after the last dose), as soon as possible after the last dose of study medication.

d Blood pressure has to be measured supine and erect to assess autonomous dysregulation (Trendelenburg test). Vital signs (to be taken before blood collection for laboratory tests) will consist of 3 pulse and 3 BP measurements (3 consecutive BP readings will be recorded at intervals of at least 1 minute).

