## **6.8 Treatment after the end of the study**

Study participants who complete the Treatment Period will have the option to transition into a dose-blinded extension study (PD0055). In this case, participants will not enter the SFU Period of PD0053. For those participants who do not roll over to PD0055, the study ends with an SFU Visit (Visit 16) approximately 30 days after the last dose. In case of early termination of a participant's study medication, the participant will be asked to attend the EOT and the SFU Visit (30 days after the last dose) and will not be eligible for PD0055.

## 7

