### **7.2           Participant Discontinuation/Withdrawal from the study**

Participants are free to withdraw from the study at any time, without prejudice to their continued care.

A participant may withdraw from the study at any time at his/her own request, or may be withdrawn at any time at the discretion of the Investigator, SMC, or DMC for safety, behavioral, compliance, or administrative reasons.

If the participant withdraws consent for disclosure of future information, the Sponsor may retain and continue to use any data collected before such a withdrawal of consent.

If a participant withdraws from the study, he/she may request destruction of any samples taken and not tested, and the Investigator must document this in the site study records.

See the Schedule of Activities (Section 1.3) for data to be collected at the time of study discontinuation and follow-up, and for any further evaluations that need to be completed. The DaT-SPECT will occur at EOT (End of Treatment), provided that the previous DaT-SPECT occurred more than 6 months prior to EOT visit.

Participants should be withdrawn from the study if any of the following events occur:

1. Withdrawal of consent by the study participant
2. A regulatory agency requests withdrawal of the participant from the study
3. Loss of ability to freely provide consent through imprisonment or involuntarily incarceration for treatment of either a psychiatric or physical (eg, infectious disease) illness or throughout quarantine conditions.

Participants must be discontinued from study medication (but not necessarily from the study) if any of the following occurs:

1. Study participant develops an illness that would interfere with his/her continued dosing.

2. Study participant takes prohibited concomitant medications as defined in the protocol. Outcome should be decided on a case-by-case basis.
3. There is confirmation of a pregnancy during the study, as evidenced by a positive pregnancy test.
4. Study participant has actual suicidal ideation since last visit as indicated by a positive response (“Yes”) to either Question 4 or Question 5 of the “Since Last Visit” version of C-SSRS. The study participant should be referred immediately to a mental healthcare professional and must be discontinued from study medication.

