## Female participants who become pregnant

- Any female participant who becomes pregnant while participating in the study will discontinue study medication.
- The Investigator will collect pregnancy information on any female participant who becomes pregnant while participating in this study. Information will be recorded on the appropriate form and submitted to the Sponsor within 1 working day of learning of a participant's pregnancy. The participant will be followed to determine the outcome of the pregnancy. The Investigator will collect follow-up information on the participant and the neonate and the information will be forwarded to the Sponsor. Generally, the follow-up will be at least 12 months after the delivery date. Any termination of pregnancy will be reported, regardless of fetal status (presence or absence of anomalies) or indication for the procedure.
- While pregnancy itself is not considered to be an AE or SAE, any pregnancy complication or elective termination of a pregnancy will be reported as an AE or SAE. A spontaneous abortion is always considered to be an SAE and will be reported as such. Any post-study pregnancy related SAE considered reasonably related to the study medication by the Investigator will be reported to the Sponsor as described in Section 8.3.5. While the

Investigator is not obligated to actively seek this information in former study participants, he or she may learn of an SAE through spontaneous reporting.

PUBLIC COPY  
This document cannot be used to support any marketing authorization application  
and any extensions or variations thereof.

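### The protocol gives two rules for study status and two safety follow-up times (14 or 30 days) when a participant becomes pregnant, with no stated order of precedence

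*Protocol*

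**What the plan says.** **Study status.** Section 8.3.5: "The participant should be withdrawn from the study as soon as pregnancy is known (by positive pregnancy test". Section 7.2 has two separate lists. The first gives three reasons for withdrawal from the study: withdrawn consent, a regulatory agency's request, and loss of the ability to consent freely. Pregnancy is not among them. The second list opens with "Participants must be discontinued from study medication (but not necessarily from the study) if any of the following occurs", and its item 3 reads "There is confirmation of a pregnancy during the study, as evidenced by a positive pregnancy test". Appendix 4 (Section 10.4), to which Section 8.3.5 sends the Investigator for procedures, says: "Any female participant who becomes pregnant while participating in the study will discontinue study medication". It does not mention study status.

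**Safety follow-up.** Section 8.3.5: "An SFU Visit should be scheduled 14 days after the participant has discontinued her study medication". Section 6.8, on early termination of study medication: "the participant will be asked to attend the EOT and the SFU Visit (30 days after the last dose". Footnote c of the Schedule of Activities, which covers every participant who terminates prematurely, asks for final evaluations "in accordance with the EOT and SFU Visit schedule (30 days after the last dose".

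**Reporting.** Section 8.3.5 requires the Sponsor to be told no later than 24 hours after the Investigator learns of the pregnancy. Appendix 4 has the information recorded on a form and "submitted to the Sponsor within 1 working day of learning of a participant's pregnancy".

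**The concern.** A pregnancy exposed to an investigational drug is a safety event that the protocol plans for. Women of childbearing potential may enrol, pregnancy tests are repeated through treatment, and outcomes are followed for at least 12 months after delivery. A site that meets the event will find different instructions in different sections, and no section says which takes precedence.

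Two consequences follow. First, the SFU date closes routine AE collection (Protocol 8.3.1), and the SAP uses it as the cut-off for calling an event treatment-emergent (SAP 5.4.2), so the choice of section changes the safety window. Second, study status determines which row of Table 9-2 applies to the participant's later efficacy data.

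**Working it through.** No sample size, power or error-rate figure is involved. The check sets the current sections side by side, with two small subtractions.

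| Point | Section 8.3.5 | Elsewhere in the protocol |
|---|---|---|
| Study status | Leaves the study | 7.2 item 3: stops study medication, may stay in the study; Appendix 4: stops study medication, study status not addressed |
| SFU Visit | 14 days after stopping study medication | 6.8 and footnote c: 30 days after the last dose, no exception for pregnancy |
| Report to Sponsor | 24 hours from learning | Appendix 4: form within 1 working day from learning |

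**Step 1, study status.** Section 7.2 deliberately separates leaving the study from stopping study medication. It places pregnancy in the second group and leaves it out of the first. Section 8.3.5 places it in the first. A site that follows the cross-reference from 8.3.5 to Appendix 4 arrives at text that requires only the drug to be stopped.

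**Step 2, SFU timing.** If the day of stopping is also the day of the last dose, the difference is 30 − 14 = 16 days. AEs are collected until the SFU Visit, and the SAP does not count an AE with onset after that visit as treatment-emergent. An event starting on days 15 to 30 after the last dose therefore falls inside the window under 6.8 and footnote c, and outside it under 8.3.5. Section 8.3.1 also asks for serious events up to 30 days after the end of the study for each participant. If her study ends at the 14-day visit, that reaches day 14 + 30 = 44. Serious events in the gap would still be collected, but by the SAP's definition they would not be treatment-emergent. Non-serious events in the gap would have no routine collection.

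**Step 3, data handling.** Protocol Table 9-2 keeps MDS-UPDRS data after treatment discontinuation (treatment policy) and sets data after study termination to missing. SAP Tables 1-2 and 1-3 draw the same line for MDS-UPDRS and DaT-SPECT. SAP 1.2.6 counts a termination as treatment-related only when the reason is lack of efficacy, so a pregnancy withdrawal would fall under other causes: missing at random for the continuous endpoints, and right-censored for the time-to-event endpoints. Each status has its own defined handling; the open question is which status applies.

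**Step 4, reporting clocks.** Both start when the pregnancy becomes known. If that is a Friday, 24 hours ends on Saturday and one working day ends on Monday, so the deadlines are about two days apart. When the next day is a working day they roughly coincide.

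**The case against.** The strongest case on the other side has four parts.

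- **Status.** Section 7.2 permits study withdrawal without requiring it, and Appendix 4 is silent, so a site that withdraws the participant under 8.3.5 breaches neither. This is correct, but it works in one direction only: a site that keeps her in the study, as 7.2 allows, departs from 8.3.5.
- **SFU timing.** Section 8.3.5 is the specific rule, and 6.8 and footnote c are general. This is a reasonable reading, but no section states the exception, and footnote c is worded to cover all premature terminations.
- **Reporting.** The 24 hours can be read as notification and the working day as submission of the form that follows. Appendix 3 treats paper SAE reports this way, since telephone notice does not replace the form. This largely stands, and for that reason the reporting times are only a minor point here. A reader might infer a flat contradiction between the clocks, or a three-day gap over a weekend. The text does not support the first, and on an ordinary weekend the deadlines are about two days apart; three days is the elapsed time from Friday to Monday.
- **Estimand.** A reader might infer that withdrawing a pregnant participant contradicts the treatment-policy handling of drug discontinuation. It does not, because Table 9-2 has separate rows for the two events. Whether scheduled efficacy visits continue after the drug is stopped is also a general question: Section 6.8 sends anyone who stops study medication early to the EOT and SFU Visits, whatever the reason.

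It should also be granted that the core safety actions agree. Sections 7.2, 8.3.5 and Appendix 4 all stop study medication, and both 8.3.5 and Appendix 4 follow the pregnancy to at least 12 months after delivery.

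**Conclusion.** The point holds for study status and for SFU timing. On status, 8.3.5 conflicts with the placement of pregnancy in 7.2. On timing, two SFU dates stand unreconciled, 16 days apart, and AE collection and the treatment-emergent cut-off move with them. The 16 days assume that stopping study medication and the last dose fall on the same day.

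For efficacy, the consequence is an ambiguity over which row of Table 9-2 applies. The reporting clocks need a clarifying sentence only. Few pregnancies are expected with enrolment at 40 to 75 years, pregnant women excluded, and contraception required. The effect on power is negligible, so this is a matter of consistent safety conduct. The documents do not show which rule was intended, and this review takes no position on that.

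**What to change.** Reconcile Section 7.2 item 3, Section 8.3.5, Section 6.8, footnote c of the Schedule of Activities and Appendix 4 so that:

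1. one rule states whether a pregnant participant leaves the study or only stops study medication;
2. one rule sets the timing of her SFU Visit, and if a pregnancy exception is intended, 6.8 and footnote c say so;
3. the text states whether the 24-hour notification and the one-working-day form submission are separate steps.

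The choice of rule is for the sponsor. The cost is protocol wording only. The SAP needs no change, because its tables already handle either status and its treatment-emergent cut-off follows the SFU date.
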